Weight, height, blood pressure, heart rate, respiration rate, and temperature will be measured by CRC nurses (pre, post). Validated questions/scales will assess demographics, medical/psychiatric history, current medications, alcohol use (AUDIT),⁷³ tobacco use (BRFSS Tobacco Use Questionnaire),^{119,120} physical activity (International Physical Activity Questionnaire),¹²¹ OHA adherence (Morisky Medication Adherence Scale-8),¹²²⁻¹²⁴ depressive symptoms (PHQ-9),^{74,75} anxiety (GAD-7),¹²⁵ hostility/anger (Buss-Perry Aggression Questionnaire),⁷⁶ trait positive affect (Positive Affect subscale of the PANAS),^{77,78} life satisfaction (Satisfaction with Life Scale),⁷⁹ insomnia symptoms (Insomnia Severity Index),⁸⁰ sleep quality (PSQI),¹²⁶ eating behaviors (Dutch Eating Behavior Questionnaire),⁸¹ quality of life (SF-20)⁸² (all pre, post), and expectancy of benefit⁸³ (pre). Attention will be determined from the intervention database for eIMPACT-DM patients and from EMR chart review for AC patients (post). Depression care variables (e.g., antidepressant dose/duration and psychotherapy session number/type) will be determined from the treatment delivery database for eIMPACT-DM patients and from EMR chart review for Active Control patients (post). Patients will complete a brief interview to assess depression care received outside of the trial (post). We will assess depression treatment acceptability (post). Diabetes prevention care received outside the trial will be assessed by EMR chart review (post) and a brief interview (post). We will also assess for the occurrence of any potential adverse events using a brief questionnaire and will administered the Techniques for Overcoming Depression Questionnaire⁸⁴ (post).

Type	Name	Time Frame	Brief Description
Hemoglobin A1c	Primary	Baseline, 6 months	The primary outcome is 6-month change in hemoglobin A1c, which will be measured at pre- and post-treatment by an immunoturbidimetric method on a Randox Daytona Clinical Analyzer in the Translation Core Analyte Lab of the Indiana CTSI. A1c is the gold standard glycemic outcome, ¹⁶ a strong predictor of future diabetes development, ^{17,18} and a potent indicator of improvement in clinical diabetes endpoints. ^{8,17,19,20}

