Treatment Process. At the end of the pre-treatment visit, our DCS will speak to the patient for 20 minutes via IU Zoom Health to orient them to depression materials and schedule the intake interview. Future DCS contacts will be over the phone or via IU Health Zoom, consistent with patient preference. Our DCS will contact the patient for the intake interview. At meetings every 2 weeks, the DCS will present cases to our team, who will formulate a Step 1 plan with PCP input. The DCS will work with the PCP to implement this plan. Step 1 will be 2 months of psychotherapy or an antidepressant. GDA and PST-PC are our first- and second-line psychotherapies; bupropion and fluoxetine are our first- and second-line antidepressants (others are third-line). For patients on an antidepressant at entry, the dosage may be increased, psychotherapy may be added, or a different antidepressant may be prescribed. For patients who want psychotherapy but have major barriers to GDA, PST-PC will be offered at Step 1. Our DCS will follow patients for 6 months, while monitoring response and staffing cases with the team at least every 2 months. At the start, the DCS will have sessions at least every 2 weeks. For patients who achieve remission ($\geq 50\%$ PHQ-9 reduction and < 3 symptoms⁵⁰), the DCS will develop a relapse prevention plan and follow-up monthly. Step 2 – augmenting Step 1 with psychotherapy or an antidepressant or switching to another psychotherapy or antidepressant – will be delivered to patients not in remission. If remission is not achieved after Step 2, Step 3 will be initiated, which will involve additional psychotherapy and/or antidepressants.

PHQ-9 Score	Action (within 24 hours)
<10 (minimal)	Results will be reported in a note added to the EMR.
10-19 (minor/moderate)	RA will encourage patient to seek treatment at their primary care clinic and will notify the patient's PCP and the embedded behavioral health clinician.
20-27 (severe)	RA will strongly encourage patient to seek treatment at their primary care clinic and will notify the patient's PCP, the embedded behavioral health clinician, and the affiliated psychiatrist.

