Active Control (AC) consists of depression education (study staff), symptom monitoring (study staff), and primary care for depression (clinical staff). (1) At the end of the pre-treatment visit, the RA responsible for Active Control delivery (a clinical psychology PhD mentee of the PI) will speak to the patient for 20 minutes via IU Zoom Health to review depression materials,¹¹⁵ including their PCP's role in its management and treatment options. In addition, patients will be provided with a list of Eskenazi

mental health services, and the RA will encourage patients to follow-up with their PCP. To engender expectancy of benefit, the RA will stress that our notifications should prompt PCP actions and that the available treatments are effective. We will then send an EMR message to the PCP indicating that their patient has a depressive disorder and was randomized to the AC group. This message will encourage the PCP to address their patient's depression, note that there are no care restrictions, and provide the same list of Eskenazi services. (2) The RA will call AC patients every 4 weeks (i.e., at the end of Months 1, 2, 3, 4, and 5) to assess depressive symptoms (PHQ-9) and will notify clinical staff to encourage additional care when indicated (see table). (3) AC patients will receive current primary care for depression. The Eskenazi primary care clinics utilize a team care approach for behavioral health issues, as PCPs are supported by embedded behavioral health clinicians and affiliated psychiatrists available for brief counseling and antidepressant management.

We chose an AC comparator¹¹⁶ for several reasons. (1) Because we plan to use an AC group in the R01-level RCT, we need to use it here to obtain accurate effect size estimates. Other approaches (no comparator or usual care comparator) could overestimate effect sizes. (2) Our AC group will help to ensure that the groups have similar expectancy of benefit and clinical

attention. We will assess expectancy⁸³ and attention and will adjust for them in a sensitivity analysis. (3) Our AC group is feasible. As eIMPACT-DM uses a flexible approach, each patient will have their own treatment path within the intervention structure. Thus, it is not possible to develop a comparator that exactly parallels the attention for each eIMPACT-DM patient.

Type	Name	Description

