Behavioral (e.g., Psychotherapy, Lifestyle Counseling)	eIMPACT-DM (intervention)	eIMPACT-DM is a 6-month, modernized, collaborative, stepped care intervention consisting of (1) computerized and telephonic cognitive-behavioral therapy for depression and (2) select antidepressant medications included in an algorithm optimized for diabetes risk reduction. It is a collaborative care intervention in which a multidisciplinary team delivers established depression treatments consistent with patient preference. It uses a stepped, flexible, treat-to-target approach that modernizes the IMPACT intervention by harnessing technology to minimize staff and space requirements. Interventions are Good Days Ahead, Problem Solving Treatment in Primary Care, and select FDA-approved antidepressants. The treatment team consists of a depression clinical specialist, a supervising MD with expertise in primary care and IMPACT, and the patients' PCPs.
Behavioral (e.g., Psychotherapy, Lifestyle Counseling)	Active Control (comparator)	Active Control (AC) consists of depression education (study staff), symptom monitoring (study staff), and primary care for depression (clinical staff). (1) The RA (a clinical psychology PhD mentee of the PI) will have a 50-minute call with AC patients to review depression materials, including their PCP's role and treatment options. We will send an EMR message to the patient's PCP to encourage the PCP to address their patient's depression. (2) The RA will call AC patients every 4 weeks to assess depressive symptoms and will notify clinical staff to encourage additional care when indicated. (3) AC patients will receive current primary care for depression. The Eskenazi primary care clinics utilize a team care approach for behavioral health issues, as PCPs are supported by embedded behavioral health clinicians and affiliated psychiatrists available for brief counseling and antidepressant management.

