11.0 Statistical Considerations

Sample Size Justification and Power Analysis

This pilot RCT is not designed to detect statistically significant differences. We chose N=64, as it is sufficient to yield the expected outcomes and is feasible within the R21 constraints. Assuming an attrition rate of $\leq 20\%$,¹¹⁷ we will have ≥ 50 completers (25/arm). With 50 completers and type I error rate=5%, we will have 55%, 68%, 79%, and 88% power to detect a $d=0.60, 0.70, 0.80$, and 0.90, respectively. We observed a $d=0.90$ for CBT for depression on fasting glucose in depressed primary care patients (see C2).

Primary Aim Analytic Plan

Analyses will use the intent-to-treat approach.¹¹⁸ Tests will be two-tailed with $p<.05$ considered statistically significant. Supplemental analyses of completers and analyses employing multiple imputation (SAS mi and mianalyze) will be performed. We will assess for group differences in baseline factors. Due to randomization, we do not expect differences. Even so, baseline differences will be taken into account when interpreting results, and baseline factors that differ between groups will be added as covariates in sensitivity analyses. We will also add expectancy and attention as covariates in sensitivity analyses.

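### Attention is measured from a different source in each arm, so the planned attention covariate is not like for like; the control-arm education contact is also printed with two durations

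*Combined protocol and SAP*

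**What the plan says.** All references are to the combined protocol and SAP.

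- **Source of attention** (3.0, Other Factors): "Attention will be determined from the intervention database for eIMPACT-DM patients and from EMR chart review for AC patients (post". No unit is given (contacts, minutes or something else).
- **Use of attention.** The rationale for the comparator in 7.0 says the team will assess expectancy and "attention and will adjust for them in a sensitivity analysis". Section 11.0 (Primary Aim Analytic Plan) repeats this: "We will also add expectancy and attention as covariates in sensitivity analyses". Neither place says how attention enters the mixed model.
- **Who delivers Active Control** (7.0). Study staff give the education and the symptom monitoring; clinic staff give the primary care. The monitoring schedule is: "The RA will call AC patients every 4 weeks (i.e., at the end of Months 1, 2, 3, 4, and 5".
- **Length of the education contact** (7.0). The narrative says the research assistant (RA) "will speak to the patient for 20 minutes via IU Zoom Health to review depression materials". The intervention table says the RA "will have a 50-minute call with AC patients to review depression materials". For the matching contact in the other arm, the text on the treatment process has "our DCS will speak to the patient for 20 minutes via IU Zoom Health to orient them to depression materials".
- **Traces in the EMR** (7.0). For a PHQ-9 score below 10, the action table says "Results will be reported in a note added to the EMR"; higher scores trigger notifications to clinic staff. A message also goes to the PCP after randomization to Active Control.
- **Clinic contact in eIMPACT-DM** (7.0, Antidepressants). The PCP writes the prescriptions and manages drug treatment jointly with the study team.

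**The concern.** The protocol accepts that its comparator cannot match the attention each eIMPACT-DM patient receives. Measuring attention and adjusting for it is the planned check on that limitation. For the check to work, a given contact must count the same way in both arms.

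Under the stated rule it does not. The intervention database mainly captures study contact in eIMPACT-DM. The chart review mainly captures clinic contact in Active Control. The method of measurement coincides with treatment assignment, so the data cannot separate a difference in attention from a difference in source. At stake is the interpretation of one planned sensitivity analysis and of the by-arm description of attention. RA minutes that are not logged at the time may also be hard to recover later.

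**Working it through.** **The plan's own figures.** The plan gives no figure for attention. Its power figures for 25 completers per arm (55%, 68%, 79% and 88% at d = 0.60, 0.70, 0.80 and 0.90) reproduce with a two-sided two-sample t-test at 5%: 54.7%, 67.9%, 79.2% and 87.7%. They contain no attention term, so this point does not touch them.

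**Step 1. What each source sees.** This reads the intervention database of 3.0 as the REDCap treatment delivery database of 7.0.

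| Contact | eIMPACT-DM | Active Control |
|---|---|---|
| Study staff | Intervention database | EMR traces only (PHQ-9 note or notification, PCP message) |
| Clinic staff | Not counted toward attention | EMR chart review |

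Scheduled study-staff contact in Active Control is 1 education contact + 5 calls = 6 per patient.

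**Step 2. Error in the between-arm gap.** Let S be study-staff contact and C clinic contact, with 1 for eIMPACT-DM and 0 for Active Control. Assume the database captures S1 fully and the chart review captures C0 fully.

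- True gap = (S1 + C1) − (S0 + C0)
- Measured gap = S1 − (counted S0 + C0)
- Error = measured − true = uncounted S0 − C1

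In contacts, the error is (0 to 6) − C1. In minutes, the call length is not stated. Assume 5 to 15 minutes per call:

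- 20-minute education contact: S0 = 20 + 5×5 = 45 to 20 + 5×15 = 95 minutes
- 50-minute education contact: S0 = 50 + 5×5 = 75 to 50 + 5×15 = 125 minutes

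The error is then (0 to 45–95) − C1 or (0 to 75–125) − C1. The documents do not give C1. The error is positive when uncounted Active Control contact exceeds C1 and negative otherwise, so its sign is not determined.

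**Step 3. What the covariate does in the model.** With both visits observed, let D be post-treatment minus pre-treatment A1c. A covariate with the same coefficient at both visits cancels from D, so D depends on treatment group alone. Under an unstructured covariance, the likelihood factors into a model for D and a model for pre-treatment A1c given D. Attention as a main effect enters only the second factor. The treatment x time estimate therefore stays equal to the difference in mean change.

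A check by simulation agrees (two visits, unstructured covariance, maximum likelihood, 25 per arm, 100 trials): the largest change on adding attention as a main effect was 3×10⁻¹⁴, which is rounding error. With 14 of 64 post-treatment values missing at random (64 − 50 completers), the largest change was 0.018 A1c percentage points.

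With an attention x time term, D is regressed on treatment group and attention, and the estimate does move. It moves by minus the fitted attention slope times the measured gap. This is where the error in step 2 enters.

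**Step 4. The two durations.** 50 − 20 = 30 minutes per patient for the same contact. The 20-minute value matches the contact with the depression clinical specialist (DCS) in the other arm. The 50-minute entry may be the one to correct, but that is an inference.

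**The case against.** The strongest reply is that little depends on this. Attention enters only a sensitivity analysis, in a pilot that the protocol says is not designed to detect significant differences. On the plainest reading, a main effect, the covariate does almost nothing to the treatment x time estimate, as step 3 shows. This stands, and it is why the point is minor. It also means that on that reading the planned adjustment does not do the job given to it.

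Second, if the unit is contacts rather than minutes, a chart review may recover much of the Active Control schedule. The PHQ-9 action table covers every score band with a note or a notification, and a PCP message follows the education contact. This stands for counts. It does not supply minutes, and it does not put eIMPACT-DM clinic contact on the same footing.

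Third, other records may exist. The database is described as including DCS notes, which need not be all it holds. The 20% fidelity audit covers Active Control with adherence checklists. The post-treatment interview on depression care outside the trial is not limited to one arm and could bear on C1. All of this is possible. However, 3.0 names the EMR as the Active Control source for attention, and none of these records is said to feed the variable or to hold RA minutes.

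A reader might infer that control-arm attention is understated and that the adjusted effect is biased in a known direction. The documents do not support this: uncounted eIMPACT-DM clinic contact works the other way, and its amount is not given.

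**Conclusion.** The point holds and is minor. The attention variable has arm-specific sources and no defined unit, so the by-arm comparison and any attention-adjusted estimate mix true and source differences. The size and direction are unknown. The only fixed quantities are the 6 scheduled study-staff contacts per Active Control patient, with no stated record of minutes, and the 30-minute conflict on one of them. The minute ranges rest on an assumed call length of 5 to 15 minutes.

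Two stronger readings go beyond the text. A reader might infer that the A1c result is compromised. It is not: the primary model has no attention term, and the d≥0.50 criterion and power are unaffected. A reader might also infer that an adjusted interval would always be too wide to be useful against the 0.3% A1c threshold. That depends on the pre-post correlation of A1c and on how far the arms differ in attention, and the documents give neither.

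A common source would make the by-arm description comparable. It would not make the adjusted estimate a causal check, because attention arises after randomization.

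**What to change.** 1. **Define attention once for both arms** (3.0): the number and total minutes of depression-related contacts from randomization to the post-treatment visit. The DCS and the RA both log study-staff contacts (date, mode, minutes) in the REDCap treatment delivery database, including the 20-minute contact at the end of the pre-treatment visit. Clinic contacts are abstracted from the EMR in both arms. Time spent on computerized CBT is reported separately.
2. **State its use** (11.0): report attention by arm. If an adjusted estimate is kept, include an attention x time term and label it exploratory because attention is post-randomization. If a common source is not possible, do not adjust for attention.
3. **Give the education contact one duration** (7.0): subject to sponsor confirmation, change the intervention table to 20 minutes via IU Zoom Health, to agree with the narrative and the DCS contact.

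The cost is a few REDCap fields for the RA, clinic-contact abstraction for about 32 eIMPACT-DM charts, one table entry, and short wording changes in 3.0 and 11.0. Section 3.0 already plans chart review of diabetes prevention care without limiting it to one arm. Depression contacts are different content, so some extra abstraction time is still needed.

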- Ongoing treatment for an inflammatory condition (e.g., rheumatoid arthritis, lupus, Crohn's disease, and ulcerative colitis) in the past 3 months (daily use of NSAIDS is allowed)
- Current pregnancy: Women able to become pregnant will complete a urine pregnancy test at the pre-treatment visit, and those with a positive pregnancy test will not continue in the trial.
- Severe cognitive impairment: ≥ 3 errors on a validated 6-item cognitive screen⁸⁷ during screening
- Acute risk of suicide: Patients will be coded as at acute risk of suicide if: (a) they trigger the Suicidal Ideation Protection Protocol (see 16.0 Appendix) during screening or at the start of the pre-treatment visit and (b) after the situation is properly handled, the patient's PCP or other clinical provider considers the patient to be at acute risk of suicide.

- History of bipolar disorder or psychosis or current use of an atypical antipsychotic medication: a self-reported diagnosis of bipolar disorder or a psychotic disorder during screening or a bipolar disorder diagnosis [ICD-9 code 296.X (all); ICD-10 codes F30X (all), F31X (all), F34.0] in the patient's EMR before enrollment or a psychotic disorder diagnosis [ICD-9 code 295.X (all); ICD-10 codes F20.X (all), F21, F22, F23, F24, F25.X (all), F29] in the patient's EMR before enrollment or current use of aripiprazole, aripiprazole lauroxil, asenapine, asenapine transdermal, brexiprazole, cariprazine, clozapine, iloperidone, lumateperone, lurasidone, olanzapine, paliperidone, paliperidone palmitate, pimavanserin, quetiapine, risperidone, or ziprasidone in the patient's EMR at screening.
- Participation in the eIMPACT Trial: All patients who participated in the eIMPACT Trial will be removed from the recruitment lists of eligible patients. Thus, none will be contacted during screening.

Inclusion of Women and Minorities

None of the inclusion/exclusion criteria of the proposed pilot RCT pertain to sex, gender, race, or ethnicity, except that pregnant women will be excluded due to the potential influence of pregnancy on depression and diabetes risk markers. We conducted a preliminary EMR search and identified 47,361 demographically and medically eligible Eskenazi primary care patients with no history of diabetes (63% women, 48% non-Hispanic Black, 20% Hispanic/Latino), of whom 9,876 (21%) fell on the high priority list (positive for a prediabetes marker). Moreover, in our eIMPACT Trial involving older Eskenazi primary care patients, we have had success recruiting and retaining racial/ethnic minorities with a depressive disorder, as 49% of the 216 randomized patients identify as non-Hispanic Black, 4.6% as Hispanic/Latino, and 3.2% as multiracial. Because <3% of Indianapolis residents are American Indian/Alaskan Native, Asian, or Native Hawaiian/Other Pacific Islander (see www.stats.indiana.edu), we do not expect these racial groups to be well-represented in the proposed trial. Based on these data, we anticipate that participants in the proposed trial will be 64 primary care patients aged ≥ 18 years with a depressive disorder and prediabetes, of whom 60% will be women, $\geq 40\%$ will be non-Hispanic Black, $\geq 10\%$ will be Hispanic/Latino. We expect that, due to randomization, groups based on sex, gender, race, and ethnicity will be approximately equally represented in the two trial arms. It is worth noting that the inclusion of a high percentage of women and racial/ethnic minorities will enhance the external validity of the findings of the proposed trial.

Inclusion of Children

Participants in the proposed pilot RCT will be 64 primary care patients aged ≥ 18 years with a depressive disorder and prediabetes. Children (<18 years) will not be eligible because a separate, age-specific study of children is warranted and preferable for at least two reasons. One, evidence indicates that depression is experienced and expressed differently in children and adolescents (e.g., with increased irritability and suicidal ideation) versus in adults. Two, the major components of our modernized collaborative stepped care intervention for depression called eIMPACT-DM – namely, Good Days Ahead (computerized cognitive-behavioral therapy), Problem-Solving Treatment in Primary Care (telephonic cognitive-behavioral therapy), and our antidepressant algorithm optimized for diabetes risk reduction – were designed for adults and have not been fully evaluated in children. Thus, the appropriateness, acceptability, and effectiveness of eIMPACT-DM in children are unknown.

